### **7.2.2 Events Specific to Post Vaccination**

Study subjects who develop joint pain, swelling or stiffness (arthralgia/arthritis) symptoms, a rash and/or small vesicles from day of vaccination until day 42 following each vaccination are instructed to notify the study site. They will be assessed by the investigator, and it will be determined if they require any additional samples collected, and/or a referral for specialist care, if needed. Specific instructions are provided to the sites in a guidance document for the assessment and work-up of these specific post vaccination events.

### **7.2.3 Reporting of Pregnancy and Lactation to the Sponsor**

Although pregnancy and lactation are not considered adverse events, it is the responsibility of investigators or their designees to report any pregnancy or lactation in a subject (spontaneously reported to them) that occurs during the trial.

Pregnancies and lactations that occur after the consent form is signed but before treatment allocation/randomization must be reported by the investigator if they cause the subject to be excluded from the trial, or are the result of a protocol-specified intervention, including but not limited to washout or discontinuation of usual therapy, diet, placebo treatment or a procedure. Pregnancies and lactations that occur from the time of treatment allocation/randomization through 42 days following any vaccination must be reported by the investigator. All reported pregnancies must be followed to the completion/termination of the pregnancy. Pregnancy outcomes of spontaneous abortion, missed abortion, benign hydatidiform mole, blighted ovum, fetal death, intrauterine death, miscarriage and stillbirth must be reported as serious events (Important Medical Events). If the pregnancy continues to term, the outcome (health of infant) must also be reported.

Such events must be reported within 24 hours to the Sponsor either by electronic media or paper. Electronic reporting procedures can be found in the EDC data entry guidelines. Paper reporting procedures can be found in the Investigator Trial File Binder (or equivalent).

#### **7.2.4 Immediate Reporting of Adverse Events to the Sponsor**

##### **7.2.4.1 Serious Adverse Events**

A serious adverse event is any adverse event occurring at any dose or during any use of Study product that:

- results in death;
- is life threatening;
- results in persistent or significant disability/incapacity;
- results in or prolongs an existing inpatient hospitalization;
- is a congenital anomaly/birth defect;
- is another important medical event.

**Note:** In addition to the above criteria, adverse events meeting either of the below criteria, although not serious per ICH definition, are reportable to the Sponsor in the same timeframe as SAEs to meet certain local requirements. Therefore, these events are considered serious by the Sponsor for collection purposes.

- Is a cancer;
- Is associated with an overdose.

Refer to Table 4 for additional details regarding each of the above criteria.

For the time period beginning when the consent form is signed until treatment allocation/randomization, any serious adverse event, or follow up to a serious adverse event, including death due to any cause, that occurs to any subject must be reported within 24 hours to the Sponsor if it causes the subject to be excluded from the trial, or is the result of a protocol-specified intervention or procedure.

For the time period beginning at treatment allocation/randomization through 365 days following first vaccination, any serious adverse event, or follow up to a serious adverse event, including death due to any cause, whether or not related to the Study product, must be reported within 24 hours to the Sponsor either by electronic media or paper. Electronic reporting

procedures can be found in the EDC data entry guidelines. Paper reporting procedures can be found in the Investigator Trial File Binder (or equivalent).

Additionally, any serious adverse event brought to the attention of an investigator who is a qualified physician at any time outside of the time period specified in the previous paragraph also must be reported immediately to the Sponsor if the event is either:

1. A death that occurs prior to the subject completing the trial, but outside the time period specified in the previous paragraph.

or

2. A serious adverse event that is considered by an investigator who is a qualified physician to be vaccine related.

All subjects with serious adverse events must be followed up for outcome.

#### **7.2.4.2 Events of Clinical Interest**

Selected non-serious and serious adverse events are also known as Events of Clinical Interest (ECI) and must be reported to the Sponsor.

For the time period beginning when the consent form is signed until treatment allocation/randomization, any ECI, or follow up to an ECI, that occurs to any subject must be reported within 24 hours to the Sponsor if it causes the subject to be excluded from the trial, or is the result of a protocol-specified intervention, including but not limited to washout or discontinuation of usual therapy, diet, placebo treatment or a procedure.

For the time period beginning at treatment allocation/randomization through 42 days following vaccination, any ECI, or follow up to an ECI, whether or not related to the Study product, must be reported within 24 hours to the Sponsor, either by electronic media or paper. Electronic reporting procedures can be found in the EDC data entry guidelines. Paper reporting procedures can be found in the Investigator Trial File Binder (or equivalent).

Events of clinical interest for this trial include:

1. An overdose of Study product, as defined in Section 7.2.1 - Definition of an Overdose for This Protocol and Reporting of Overdose to the Sponsor, that is not associated with clinical symptoms or abnormal laboratory results.

#### **7.2.5 Evaluating Adverse Events**

An investigator who is a qualified physician will evaluate all adverse events with respect to the elements outlined in Table 4. The investigator's assessment of causality is required for each adverse event. Refer to Table 4 for instructions in evaluating adverse events.

Table4: Evaluating Adverse Events

Maximum Intensity	Mild	awareness of sign or symptom, but easily tolerated (for pediatric trials, awareness of symptom, but easily tolerated)
	Moderate	discomfort enough to cause interference with usual activity (for pediatric trials, definitely acting like something is wrong)
	Severe	incapacitating with inability to work or do usual activity (for pediatric trials, extremely distressed or unable to do usual activities) Injection site redness or swelling from the day of vaccination (D0) through Day 14 post-vaccination will be evaluated by maximum size.
Seriousness	A serious adverse event (AE) is any adverse event occurring at any dose that:	
	†Results in death; or	
	†Is life threatening; or places the subject, in the view of the investigator, at immediate risk of death from the event as it occurred [Note: This does not include an adverse event that, had it occurred in a more severe form, might have caused death.]; or	
	†Results in a persistent or significant disability/incapacity (substantial disruption of one's ability to conduct normal life functions); or	
	†Results in or prolongs an existing inpatient hospitalization (hospitalization is defined as an inpatient admission, regardless of length of stay, even if the hospitalization is a precautionary measure for continued observation. (Note: Hospitalization for an elective procedure to treat a pre-existing condition that has not worsened is not a serious adverse event. A pre-existing condition is a clinical condition that is diagnosed prior to the use of study product and is documented in the patient's medical history.); or	
	†Is a congenital anomaly/birth defect (in offspring of subject taking the product regardless of time to diagnosis); or	
	Is a cancer (although not serious per ICH definition, is reportable to the Sponsor within 24 hours to meet certain local requirements; or	
	Is associated with an overdose (whether accidental or intentional). Any adverse event associated with an overdose is considered a serious adverse event for collection purposes. An overdose that is not associated with an adverse event is considered a non-serious event of clinical interest and must be reported within 24 hours.	
	Other important medical events that may not result in death, not be life threatening, or not require hospitalization may be considered a serious adverse event when, based upon appropriate medical judgment, the event may jeopardize the subject and may require medical or surgical intervention to prevent one of the outcomes listed previously (designated above by a †).	
Duration	Record the start and stop dates of the adverse event. If less than 1 day, indicate the appropriate length of time and units	
Action taken	Did the adverse event cause the test vaccine to be discontinued?	
Relationship to test vaccine	Did the test vaccine cause the adverse event? The determination of the likelihood that the test vaccine caused the adverse event will be provided by an investigator who is a qualified physician. The investigator's signed/dated initials on the source document or worksheet that supports the causality noted on the AE form, ensures that a medically qualified assessment of causality was done. This initialed document must be retained for the required regulatory time frame. The criteria below are intended as reference guidelines to assist the investigator in assessing the likelihood of a relationship between the test vaccine and the adverse event based upon the available information.	
	The following components are to be used to assess the relationship between the test vaccine and the AE; the greater the correlation with the components and their respective elements (in number and/or intensity), the more likely the test vaccine caused the adverse event:	
	Exposure	Is there evidence that the subject was actually exposed to the test vaccine such as: reliable history, acceptable compliance assessment (e.g., diary), seroconversion or identification of vaccine virus in bodily specimen?
	Time Course	Did the AE follow in a reasonable temporal sequence from administration of the test vaccine? Is the time of onset of the AE compatible with a vaccine-induced effect?
	Likely Cause	Is the AE not reasonably explained by another etiology such as underlying disease, other drug(s)/vaccine(s), or other host or environmental factors

Relationship to test vaccine (continued)	The following components are to be used to assess the relationship between the test vaccine and the AE: (continued)	
	Dechallenge	(not applicable for vaccines)
	Rechallenge	
Was the subject reexposed to the test vaccine in this trial? If yes, did the AE recur or worsen? If yes, this is a positive rechallenge. If no, this is a negative rechallenge. (Note: This criterion is not applicable if: (1) the initial AE resulted in death or permanent disability, or (2) the trial is a single-dose vaccine trial.) NOTE: IF A RECHALLENGE IS PLANNED FOR AN ADVERSE EVENT WHICH WAS SERIOUS AND WHICH MAY HAVE BEEN CAUSED BY THE TEST VACCINE, OR IF REEXPOSURE TO THE TEST VACCINE POSES ADDITIONAL POTENTIAL SIGNIFICANT RISK TO THE SUBJECT, THEN THE RECHALLENGE MUST BE APPROVED IN ADVANCE BY THE SPONSOR CLINICAL DIRECTOR AND THE INSTITUTIONAL REVIEW BOARD/INDEPENDENT ETHICS COMMITTEE.

	Consistency with Trial Vaccine Profile	Is the clinical/pathological presentation of the AE consistent with previous knowledge regarding the test vaccine or vaccine class pharmacology or toxicology?

The assessment of relationship will be reported on the case report forms /worksheets by an investigator who is a qualified physician according to his/her best clinical judgment, including consideration of the above elements.

Record one of the following:	Use the following criteria as guidance (not all criteria must be present to be indicative of a vaccine relationship).
Yes, there is a reasonable possibility of vaccine relationship.	There is evidence of exposure to the test vaccine. The temporal sequence of the AE onset relative to the administration of the test vaccine is reasonable. The AE is more likely explained by the test vaccine than by another cause.
No, there is not a reasonable possibility of vaccine relationship	Subject did not receive the test vaccine OR temporal sequence of the AE onset relative to administration of the test vaccine is not reasonable OR the AE is more likely explained by another cause than the Study product. (Also entered for a subject with overdose without an associated AE.)

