#### 4.3.1.3 Reactions to V920

Detailed safety data collected in the Phase 2 and 3 studies to date have demonstrated V920 to be generally well-tolerated when administered to healthy, non-pregnant, adults. Injection site reactions following vaccination are generally mild to moderate and self-limited. Thereafter, there is a predictable period of early reactogenicity, including fever and a flu-like syndrome and resolves with 7 days. During this time, transient decreases in white blood cells and platelets

have also been observed but bleeding or increased risk of infection has not been reported. The early reactogenicity is likely to be a result of viremia with the vaccine virus which resolves within 2 weeks. Vaccine virus has been found in saliva, urine, and skin-vesicles in vaccines. Person-to-person transmission has not been documented, however transmission through shedding and close personal contact is accepted as a theoretical possibility. Joint pain (arthralgia) is part of the early flu-like syndrome in the first week after vaccination in up to 44% of vaccines. In a small proportion of subjects (<5%), joint swelling (arthritis) may develop in the 2nd to 3rd week after vaccination. The arthritis is thought to be virally-mediated, and while the majority of arthralgia and arthritis events resolved spontaneously, recurrent or persistent arthralgia and arthritis have also been reported. The safety profile reported from the Ebola-epidemic region has been similar to that observed outside the region.

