#### **7.2 Assessing and Recording Adverse Events**

An adverse event is defined as any untoward medical occurrence in a patient or clinical investigation subject administered a pharmaceutical product and which does not necessarily have to have a causal relationship with this treatment. An adverse event can therefore be any unfavorable and unintended sign (including an abnormal laboratory finding, for example), symptom, or disease temporally associated with the use of a medicinal product or protocol-specified procedure, whether or not considered related to the medicinal product or protocol-specified procedure. Any worsening of a preexisting condition that is temporally associated with the use of the Study product, is also an adverse event.

Changes resulting from normal growth and development that do not vary significantly in frequency or severity from expected levels are not to be considered adverse events. Examples of this may include, but are not limited to, onset of menses or menopause occurring at a physiologically appropriate time.

Study product includes any pharmaceutical product, biological product, device, diagnostic agent or protocol-specified procedure, whether investigational (including active control medication) or marketed (including normal saline placebo), provided by or distributed by the Sponsor for human use in this study.

Adverse events may occur during clinical trials, or as prescribed in clinical practice, from overdose (whether accidental or intentional), from abuse and from withdrawal.

All adverse events that occur after the consent form is signed but before allocation/randomization must be reported by the investigator if they cause the subject to be excluded from the trial, or are the result of a protocol-specified intervention, including but not limited to study procedures. From the time of allocation/randomization through 42 days following each vaccination, all adverse events must be reported by the investigator. Such events will be recorded at each examination on the Adverse Event case report forms/worksheets. The reporting timeframe for adverse events meeting any serious criteria is described in section 7.2.3.1. The investigator will make every attempt to follow all subjects with non-serious adverse events for outcome.

Electronic reporting procedures can be found in the Electronic Data Capture (EDC) data entry guidelines. Paper reporting procedures can be found in the Investigator Trial File Binder (or equivalent).

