#### Vaccine reactogenicity

Counts and percentages of solicited local and systemic reaction frequency and severity among study cohorts (various CD4 counts and ages) will be summarized.

Adverse events will be classified by Medical Dictionary for Regulatory Activities (MedDRA®) system organ class and preferred term, severity, seriousness, investigator causality assessment, and time since vaccination.

Safety listings will display all safety events, including a separate display of solicited post-treatment reactions, and all other AEs.

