Lymphocytes Decrease - cell/mm 	750 – 1,000	500 – 749	250 – 499	< 250
Neutrophils Decrease - cell/mm 	1,500 – 2,000	1,000 – 1,499	500 – 999	< 500
Eosinophils - cell/mm 	650 – 1500	1501 - 5000	> 5000	Hypereosinophilic
Platelets Decreased - cell/mm 	125,000 – 140,000	100,000 – 124,000	25,000 – 99,000	< 25,000
PT – increase by factor (prothrombin time)	1.0 – 1.10 x ULN**	1.11 – 1.20 x ULN	1.21 – 1.25 x ULN	> 1.25 ULN
PTT – increase by factor (partial thromboplastin time)	1.0 – 1.2 x ULN	1.21 – 1.4 x ULN	1.41 – 1.5 x ULN	> 1.5 x ULN
Fibrinogen increase - mg/dL	400 – 500	501 – 600	> 600	--
Fibrinogen decrease - mg/dL	150 – 200	125 – 149	100 – 124	< 100 or associated with gross bleeding or disseminated intravascular coagulation (DIC)
Urine *				
Protein	Trace	1+	2+	Hospitalization or dialysis
Glucose	Trace	1+	2+	Hospitalization for hyperglycemia

Blood (microscopic) - red blood cells per high power field (rbc/hpf)	1 - 10	11 - 50	> 50 and/or gross blood	Hospitalization or packed red blood cells (PRBC) transfusion
--	--------	---------	-------------------------	--

\* The laboratory values provided in the tables serve as guidelines and are dependent upon institutional normal parameters. Institutional normal reference ranges should be provided to demonstrate that they are appropriate.

\*\* The clinical signs or symptoms associated with laboratory abnormalities might result in characterization of the laboratory abnormalities as Potentially Life Threatening (Grade 4). For example, a low sodium value that falls within a grade 3 parameter (125-129 mE/L) should be recorded as a grade 4 hyponatremia event if the subject had a new seizure associated with the low sodium value.

\*\*\*"ULN" is the upper limit of the normal range.

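### Section 7.2.5 grades all adverse events on Table 4's symptom and function scale, Appendix 2 grades laboratory values by number, and nothing says which governs laboratory adverse events

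*Combined protocol and SAP*

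**What the plan says.** **Definition.** Section 7.2 lets an adverse event be "any unfavorable and unintended sign (including an abnormal laboratory finding, for example".

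**Scale named for adverse events.** Section 7.2.5 states: "An investigator who is a qualified physician will evaluate all adverse events with respect to the elements outlined in Table 4". It makes no exception for laboratory events and does not mention Appendix 2. Table 4's Maximum Intensity levels are:
- mild: "awareness of sign or symptom, but easily tolerated"
- moderate: "discomfort enough to cause interference with usual activity"
- severe: "incapacitating with inability to work or do usual activity"

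There is no fourth level. The one measured element is injection-site redness or swelling, which is judged by maximum size through Day 14.

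**Scale in the appendix.** Appendix 2 has four numeric grades, the third labelled severe and the fourth potentially life-threatening. A footnote on sodium says that a low value "should be recorded as a grade 4 hyponatremia event if the subject had a new seizure associated with the low sodium value". Another footnote describes the values as guidelines that depend on institutional normal parameters.

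**Analysis.** Section 8.2.5.2 classifies adverse events by "system organ class and preferred term, severity, seriousness, investigator causality assessment, and time since vaccination". Under its heading for vital signs and laboratory measures it gives means and standard deviations by treatment group, says that shift tables may be produced, and leaves extreme values to individual discussion. Section 4.2.3.2 makes the occurrence of any haematological or biochemical abnormality a primary safety endpoint, with no grade or threshold.

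**Expected effect.** Section 4.3.1.3 reports that after V920 transient decreases in white cells and platelets "have also been observed but bleeding or increased risk of infection has not been reported".

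**The concern.** A laboratory value has a severity whether or not the subject notices it. Table 4 has no means of rating one that goes unnoticed, and Section 7.2.5 names Table 4 alone. Appendix 2 can rate it, but no operative section gives the appendix a role in grading adverse events.

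White cell and platelet falls are a described effect of V920, and they are described as occurring without bleeding or extra infection. A symptom scale says least about that kind of event. Section 4.2.1 notes that V920 has not been formally evaluated in HIV-infected people in a randomised way, so how deep these falls go here is part of the first primary objective.

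The trial runs at four sites in three countries. Without a governing rule, one site could grade a laboratory event on Table 4 and another on Appendix 2. Section 5.4 stratifies randomisation by site, so this need not bias the comparison between arms. It would, however, make pooled severity percentages hard to interpret and could hide a difference between arms.

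**Working it through.** The plan states no figure on this point to reproduce. The check sets the passages side by side.

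**Step 1. Are laboratory findings within the reach of Table 4?** Section 7.2 says that an adverse event can be an abnormal laboratory finding. Section 7.2.5 sends all adverse events to Table 4. So any laboratory finding reported as an adverse event goes to Table 4. Section 7.2 does not make every abnormal value an adverse event.

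**Step 2. Apply both scales to the same subject, who has no symptoms.** Cell counts are per mm³.

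| Value | Appendix 2 band | Appendix 2 grade | Table 4 level |
|---|---|---|---|
| Platelets 30,000 | 25,000 to 99,000 | 3, severe | mild at most, or none |
| Neutrophils in the band shown | 500 to 999 | 3, severe | mild at most, or none |
| White cells 900 | below 1,000 | 4, potentially life-threatening | mild at most, or none |

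Moderate needs discomfort that interferes with activity and severe needs incapacity, so neither can be met without symptoms. Mild needs awareness of a sign or symptom, so a subject who is unaware of anything may fit no level.

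**Step 3. Size of the discordance.** Counting mild as level 1, Grade 3 is 3 − 1 = 2 levels higher and Grade 4 is 4 − 1 = 3 levels higher. Table 4 has no level for Grade 4. For scale, the screening limit in Section 5.1.3 is a platelet count of at least 125,000. A later count of 60,000 is then at most 60,000/125,000 = 48% of the screening value, a fall of at least 52%. It lies in the Grade 3 band and still reaches no more than mild on Table 4 if there are no symptoms.

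**Step 4. Does any text choose between the scales?** No operative section cites Appendix 2 or maps four grades onto three levels. Apart from the table of contents, it is cited only in the amendment history, in the Amendment 8 entry on exclusion criteria. That entry concerns eligibility. It says that the toxicity grading scales are directed at healthy populations and are not applicable to this HIV-infected population.

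**Step 5. Does the separate laboratory analysis report depth by grade?** The primary endpoint concerns the occurrence of abnormalities. Means and standard deviations do not count occurrences, and a few deep falls can disappear in a mean. Shift tables are optional, and what makes a value extreme is not defined. No tabulation by Appendix 2 grade is planned.

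**The case against.** The strongest reply is that the two texts can be read together. Appendix 2 labels its first three grades with Table 4's own words, and its sodium footnote speaks of recording an event by grade. On that reading Appendix 2 supplies the laboratory anchors for Table 4's terms, and only a cross-reference is missing. The reading is plausible, but Section 7.2.5 does not say it, Grade 4 has no counterpart in Table 4, and the appendix calls its values guidelines. Reporting procedures are also deferred to data-entry guidelines and a site binder that are not in the documents, so actual coding practice is unknown.

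Second, laboratory falls are not lost. They are a primary endpoint of their own, extreme values are to be discussed individually, and the listings show all safety events. This stands, and it limits the harm to how severity is classified and summarised.

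Third, Appendix 2 may not suit this population: its own footnote and the Amendment 8 rationale both qualify it. This stands too, and it shapes the fix.

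Some stronger readings are tempting, and the documents do not support them:
- *Asymptomatic severe falls are recorded as mild.* No section says so. They may fit no Table 4 level, and the sodium footnote points towards numeric grades.
- *Every adverse event is graded by how the subject feels.* Injection-site redness and swelling go by size, and the upper levels also rest on function.
- *V920 is known to cause Grade 3 or 4 falls.* Section 4.3.1.3 reports transient decreases and gives no grade.
- *Stopping is compromised.* The rules in Appendix 3 turn on death, on life-threatening or serious related events, or on investigator or committee opinion. None uses the intensity level.

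**Conclusion.** The point holds as an unresolved conflict between two severity scales. Followed literally, Section 7.2.5 cannot rate an asymptomatic cytopenia above mild, while Appendix 2 may call the same value severe or potentially life-threatening. The severity classification in Section 8.2.5.2 is therefore discordant for laboratory events by two or three levels. The committed laboratory summaries do not replace it for a primary endpoint about the occurrence of abnormalities.

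How many events would be affected cannot be derived, because the documents give no rate of graded cytopenia. The conclusion assumes that at least some laboratory findings are reported as adverse events and that no document outside the set settles the scale. The values themselves are kept and the stopping triggers do not change, so this is a change that should be made and not a threat to the trial's validity.

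**What to change.** 1. **Reconcile the passages.** State in Table 4 (Maximum Intensity) and in Section 8.2.5.2 that laboratory adverse events are graded on a numeric laboratory scale from 1 to 4, and that the symptom and function scale applies to clinical events. Keep the size rule for injection-site redness and swelling.
2. **Confirm the scale.** The sponsor should confirm that Appendix 2 suits the local reference ranges and an HIV-infected population, or name the numeric scale to be used instead, and should cite it in Section 7.2.5.
3. **Commit to the tabulation.** In Section 8.2.5.2, replace the optional shift tables with two planned tables by arm: post-vaccination laboratory abnormalities by worst numeric grade, and shift from baseline grade.

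The flow charts already schedule haematology and chemistry at screening, on Day 0 and through Day 42 after each vaccination, so grades can be derived from data already collected. The cost is a few sentences and a little more analysis. Some laboratory events will appear at a higher severity than Table 4 would give, and the report should explain that.
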